#### 2.2.4 *Sample Size Determination*

Approximately 30 subjects will be randomized in a 2:1 ratio to 1 of 2 treatment groups: ADX-629 or placebo, both with standard of care treatment for COVID-19. This clinical trial is exploratory in nature and is not formally powered.

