## 3.4 Efficacy Assessment

Efficacy data (i.e., secondary endpoints) will be analyzed by randomized treatment based on the ITT Population. The key efficacy endpoint will also be analyzed based on the PP Population. The trial is exploratory and not formally powered. All assessments will be deemed exploratory.

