**Table 1. NIAID 8 Point Ordinal Scale for COVID 19**

Numerical Score	Definition
1	Death

2	Hospitalized, on invasive mechanical ventilation or extracorporeal membrane oxygenation
3	Hospitalized, on noninvasive ventilation or high-flow oxygen devices
4	Hospitalized, requiring supplemental oxygen
5	Hospitalized, not requiring supplemental oxygen – requiring ongoing medical care (COVID-19 related or otherwise)
6	Hospitalized, not requiring supplemental oxygen – no longer requires ongoing medical care
7	Not hospitalized, limitation on activities and/or requiring home oxygen
8	Not hospitalized, no limitation on activities

NIAID scores change from baseline to Day 28 will be summarized by treatment group (ADX-629 or placebo) using descriptive statistics (n, mean, standard deviation, median, minimum, and maximum).

All NIAID data will be listed.

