### 3.4.2 Other Efficacy Endpoints

Additional efficacy endpoints include the following:

- Proportion of subjects alive and not mechanically ventilated over Day 1 through Day 28;
- Time to recovery (for hospitalized subjects at Screening), defined as the first day on which the subject has an NIAID score of 6 or larger;
- Time to recovery (for non-hospitalized subjects at Screening), defined as the second consecutive day on which the subject has an improvement in the NIAID ordinal scale by 1 point;
- Proportion of subjects alive and not in the intensive care unit over Day 1 through Day 28;
- Proportion of subjects alive and not in the hospital over Day 1 through Day 28;

- Proportion of subjects alive and not on supplemental oxygen over Day 1 through Day 28;
- Mortality; and
- Time to hospital discharge (for hospitalized subjects), defined as time from first hospital admission to first hospital discharge in the 28 day study period.

The proportions will be presented by treatment group (ADX-629 or placebo). The difference between treatment groups will be analyzed by a Generalized Estimating Equation (GEE) model similar to the MMRM model for the key efficacy endpoint if applicable. If the GEE model does not converge, then the Fisher's exact test will be used.

Time to recovery (censored at Day 28) from randomization and time to hospital discharge will be addressed by Kaplan-Meier analysis, including a comparison between the treatment groups by a log-rank test if applicable.

The mortality rate, calculated as the number of subjects who died by Day 28 divided by the number of subjects randomized, will be summarized by treatment group. The difference between treatment groups will be analyzed by Fisher's exact test if applicable.

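### The GEE comparison in SAP 3.4.2 rests on about 20 versus 10 subjects with no small-sample correction; in its usual uncorrected Wald form, a nominal 5% test would reject a true null roughly 8-14% of the time when daily event-free proportions are about 0.8-0.9

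*SAP*

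**What the plan says.** SAP 2.2.4 sets the size: "Approximately 30 subjects will be randomized in a 2:1 ratio to 1 of 2 treatment groups". It adds: "This clinical trial is exploratory in nature and is not formally powered".

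For the four daily-status proportions, SAP 3.4.2 says: "The difference between treatment groups will be analyzed by a Generalized Estimating Equation (GEE) model", to be built like the MMRM for the key endpoint and qualified by 'if applicable'. The only safeguard is: "If the GEE model does not converge, then the Fisher's exact test will be used".

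The MMRM used as the template is not described. SAP 3.4.1 gives only this for the key endpoint: "NIAID scores change from baseline to Day 28 will be summarized by treatment group (ADX-629 or placebo) using descriptive statistics". Link, working correlation, variance estimator, test statistic, reference distribution and significance level are therefore all unstated. Protocol 9.2.1 refers to the SAP for specific methods, and SAP 7 leaves programming detail to a separate document. On status, SAP 3.4 says: "All assessments will be deemed exploratory".

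**The concern.** Treatment varies between subjects. Scoring up to 28 days per subject adds rows but no independent units, so the treatment contrast rests on about 10 placebo and 20 active subjects. With so few clusters the ordinary sandwich standard error tends to be too small, and a normal reference makes the test more liberal still.

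The Fisher fallback guards against a different failure. A model can converge, look normal and still give a standard error that is too small; Fisher's test is then never triggered. At stake are p-values for efficacy endpoints that look stronger than the data support.

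**Working it through.** The plan gives no power, significance level or event rate, so there is no figure of its own to reproduce. The check simulates a true null.

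**Inputs from the documents**
- Arms: 30 × 2/3 = 20 and 30 × 1/3 = 10 (SAP 2.2.4).
- Daily status on Days 1 to 28 (SAP 2.2.1).
- ITT Population (SAP 3.4).

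**Assumptions**
- The 28 daily values are the GEE data, with no missing days.
- Logit link, uncorrected sandwich variance, two-sided Wald z at 1.96.
- Daily event-free probability p from 0.5 to 0.95, the same in both arms.
- Three within-subject patterns: beta-binomial, day-to-day Markov, and spells of varying length.

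**Formula.** With equal days per subject and treatment only, let yᵢ be subject i's share of event-free days and m_g the mean in arm g:

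θ = logit(m_A) − logit(m_P)

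V = Σ_g [Σᵢ(yᵢ − m_g)² / n_g²] / [m_g(1 − m_g)]²

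Reject if |θ/√V| > 1.96.

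Mancl-DeRouen multiplies each arm's term by [n_g/(n_g − 1)]², which is (10/9)² = 1.235 for placebo and (20/19)² = 1.108 for active, and is used here with t on 28 df (2.048). If placebo carries two thirds of the variance, the interval widens by √(2/3 × 1.235 + 1/3 × 1.108) × 2.048/1.96 = 1.092 × 1.045 = 1.14, or about 14%.

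**Null rejection (%)**, 40,000 trials per scenario, among trials with a finite estimate. The last column is the case where a subject's outcome never changes; the other columns exclude it.

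| p | Uncorrected Wald | Mancl-DeRouen, t(28) | Robust score | Wald, constant within subject |
|---|---|---|---|---|
| 0.5 | 5.1-7.1 | 2.5-4.2 | 5.1-5.4 | 4.4 |
| 0.7 | 6.0-8.3 | 3.6-5.3 | 5.1-5.6 | 2.5 |
| 0.8 | 7.6-9.3 | 4.6-6.7 | 5.1-6.0 | 1.7 |
| 0.9 | 9.3-14.4 | 6.0-11.0 | 1.8-5.5 | 0.6 |
| 0.95 | 9.4-17.0 | 6.3-12.3 | 0.2-5.4 | 0.1 |

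**Fitted models.** A GEE with a day term (within-subject correlation 0.5, 500 trials, exchangeable and independence) gave 5.6-6.6% at p = 0.6, 8.6-9.0% at 0.8 and 14.8-15.7% at 0.9. Simulation error at 0.9 is about √(0.15 × 0.85/493) = 1.6 points.

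**Patterns shaped like the endpoints**
- Oxygen-type (20-50% ever on oxygen), 6,000 trials each: 10.0-13.1%.
- Hospital-type (30-100% inpatient at start), 6,000 trials each: 8.4-9.5%.
- Across these, the robust SE relative to the true SD of the log odds ratio ran from 1.037/1.329 = 0.78 to 0.386/0.418 = 0.92, so it was 22% to 8% too small.
- A fitted exchangeable GEE with treatment and day (1,500 trials each) gave 10.3% for oxygen and 9.5% for hospital. Mancl-DeRouen with t(28) gave 6.7% and 3.6%. A permutation test on event-free days gave 4.6% and 4.5%.
- With all subjects event-free on Day 1 and 10-50% later having one spell (mean 5 or 10 days; 20,000 trials), Wald gave 8.6-11.8% and the permutation test 1.8-4.3%.

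**Sparse endpoints.** If a fraction q of subjects is ever affected, the chance that at least one arm has no events is 1 − [1 − (1 − q)²⁰][1 − (1 − q)¹⁰]. At q = 0.10 this is 1 − 0.878 × 0.651 = 43%. At q = 0.05 it is 1 − 0.642 × 0.401 = 74%.

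**The case against.** The strongest reply is that the SAP does not choose an uncorrected Wald test; it is silent. A robust score test would hold its size, the separate programming document may specify a correction, and the GEE is itself conditional. A proportion over Day 1 through Day 28 with a Fisher fallback can even be read as one outcome per subject, for which the simulated excess disappears (last column of the table). All of this stands, and it makes the error rate conditional. It does not remove the gap: the SAP should fix the test, and its one safeguard does not address this failure.

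Three stronger readings are tempting and are not supported.
- A reader might infer that the planned test has a false-positive rate of 8-14% as a matter of fact. Across the scenarios and test forms tried, rates ran from about 0% to 17%.
- A reader might infer that reported intervals will be too narrow. The SAP plans none for these proportions.
- A reader might infer that all four endpoints are shown to be affected. Protocol 4.2 excludes NIAID scores below 5, high-flow oxygen and noninvasive ventilation, so ventilation and intensive-care events may be rare. There the no-events problem may dominate.

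The exploratory label also counts. There is no decision rule, the primary objective is safety, and nothing in the documents says that these p-values decide further development.

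**Conclusion.** The concern holds in conditional form. SAP 3.4.2 leaves the GEE test unspecified at about 20 versus 10 subjects, and its convergence rule cannot catch an understated standard error. Given an uncorrected sandwich Wald test at two-sided 5%, complete data and outcomes that vary within subjects, null rejection is roughly 8-14% at daily event-free proportions of 0.8-0.9. A Wald interval built the same way would cover about 86-92% instead of 95%. Near 0.5-0.7 the rate is about 5-8%. The result applies to oxygen- and hospital-type patterns when both arms have events. It is worth correcting because the change is cheap, but the consequence is limited in an exploratory, unpowered trial.

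**What to change.** In SAP 3.4.2, before database lock:

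- Make the between-arm test a permutation (re-randomization) test that follows the allocation scheme actually used. The statistic is either the GEE treatment contrast or the difference in mean days (0-28) alive and event-free, with days after death counted as not free. The day-count form stays defined when an arm has no events.
- State a rule for missing days, including those after withdrawal.
- If an interval is wanted, invert the permutation test. A percentile bootstrap is not a safe substitute: in 2,000 simulated trials per assumed spell pattern, with events in both arms, it missed a true zero difference 5.9-9.8% of the time.
- Keep the daily proportions by arm as the descriptive display.
- If the GEE stays, label it supportive. State its link, working correlation and covariates, and use a small-sample corrected variance such as Mancl-DeRouen with a t reference. Note that excess error remains near 1 (6-11% at a daily proportion of 0.9).

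The cost is a paragraph of SAP text, minor programming and less favourable p-values. With the day-count form, the tested quantity becomes a per-subject summary instead of the protocol's proportion.

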4.3 Withdrawal Criteria

Participation of a subject in this clinical trial may be discontinued for any of the following reasons:

- Withdrawal of consent or a subject request for discontinuation from the clinical trial for any reason;
- Occurrence of any medical condition or circumstance that exposes the subject to substantial risk and/or does not allow the subject to adhere to the requirements of the protocol;
- Any SAE, clinically significant AE, severe laboratory abnormality, intercurrent illness, or other medical condition which indicates to the Investigator that continued participation is not in the best interest of the subject;
- Pregnancy;
- Requirement of prohibited concomitant medication;
- Subject failure to comply with protocol requirements or clinical trial-related procedures; or
- Termination of the clinical trial by the Sponsor or the regulatory authority.

Unless a subject withdraws consent for further follow-up, subjects who discontinue study drug (ADX-629 or placebo) will continue with the clinical trial for acquisition of safety and efficacy assessments through the Day 60 telephone follow-up visit. If a subject withdraws prematurely from

the clinical trial prior to the EOT visit (Day 28), clinical trial staff should make every effort to complete the full panel of assessments scheduled for the EOT visit (Day 28). The reason for subject withdrawal must be documented in the electronic case report form (eCRF).

Withdrawn subjects will not be replaced.

[figure not shown]

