6.5 Telephone Follow-Up (Day 60)

All subjects will undergo a telephone follow-up visit at Day 60. The purpose of the telephone follow-up is to assess survival status and evaluate for COVID-19 relapse. The following procedures will be performed during the telephone follow-up (Day 60):

- Record concomitant medications; and
- Record AEs.

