6.6 Early Termination Visit and Withdrawal Procedures

The EOT for subjects completing the clinical trial is Day 28. For subjects who are withdrawn from the clinical trial prior to completion, all Day 28 procedures (see Section 6.3.10) will be performed at an early termination visit. Subjects who are withdrawn and complete an early termination visit will also undergo a telephone follow-up at Day 60.

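### The SAP mortality rate counts every subject of unknown Day 28 vital status as a survivor, and Protocol 6.5 and 6.6 are not aligned on who is called to establish survival

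*SAP*

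**What the plan says.** SAP 3.4.2 lists mortality among the other efficacy endpoints. The rate is "calculated as the number of subjects who died by Day 28 divided by the number of subjects randomized", and "The difference between treatment groups will be analyzed by Fisher's exact test if applicable". The same section uses Kaplan-Meier for time to recovery and time to hospital discharge, but not for death. Nowhere does the SAP give a censoring, imputation, exclusion or sensitivity rule for a subject whose vital status at Day 28 is not known.

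The protocol bears on how often that will happen:

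- Section 4.3, subjects who only stop study drug: "Unless a subject withdraws consent for further follow-up, subjects who discontinue study drug (ADX-629 or placebo) will continue with the clinical trial", with assessments through the Day 60 call.
- Section 4.3, subjects who leave the trial early: staff are asked to make every effort to obtain the Day 28 panel. Also, "Withdrawn subjects will not be replaced".
- Section 6.4: all subjects have a Day 35 visit, by telephone if they cannot attend.
- Section 6.5: "All subjects will undergo a telephone follow-up visit at Day 60". On why the call is made: "The purpose of the telephone follow-up is to assess survival status and evaluate for COVID-19 relapse". The procedures listed are recording concomitant medications and recording AEs.
- Section 6.6: "Subjects who are withdrawn and complete an early termination visit will also undergo a telephone follow-up at Day 60". It says nothing about withdrawn subjects who miss that visit.

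**The concern.** Dividing deaths by all randomized is sound when every vital status is known. When one is not, the formula silently imputes survival, and Fisher's test treats that imputed survivor as observed.

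Loss of follow-up could be related to outcome. The reasons in Protocol 4.3 for ending participation include SAEs, severe laboratory abnormalities and intercurrent illness. The early termination visit in 6.6 comprises all the Day 28 procedures, which a very ill subject may be unable to complete. If unknown statuses fall unevenly between arms, the reported mortality difference shifts in favour of the arm with proportionally more of them.

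The Day 60 call is the natural place to recover Day 28 status after the fact. A site reading 6.6 alone could conclude that a withdrawn subject who missed the early termination visit need not be called. A site following the 6.5 procedure list has no item in which to enter vital status or the date last known alive. Safety is the primary objective of this trial, so a reader will look at the mortality line even though it sits among the secondary endpoints.

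**Working it through.** The plan states no mortality, dropout or power figure, so there is nothing to reproduce. The check evaluates the SAP formula.

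**Inputs from the documents.** About 30 subjects, allocated 2:1 (SAP 2.2.4): 30 × 2/3 = 20 on ADX-629 and 30 × 1/3 = 10 on placebo. Rate and test as in SAP 3.4.2.

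**Inputs assumed.** Known deaths *d* and unknown vital statuses *u* in each arm.

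**Formulas**, with *n* randomized:

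- SAP rate: *d*/*n*
- Known status only: *d*/(*n* − *u*)
- All unknowns dead: (*d* + *u*)/*n*

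**Effect of one unknown.** It adds 1 to *n* and 0 to *d*, exactly as a survivor does. If that subject in fact died, the rate is understated by 1/20 = 5 percentage points on ADX-629 or 1/10 = 10 points on placebo. With *u* = 0 all three formulas agree.

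**Illustration A: one known death and two unknowns in each arm**

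| Treatment of unknowns | ADX-629 | Placebo | Fisher p (two-sided) |
|---|---|---|---|
| SAP: all counted alive | 1/20 = 5% | 1/10 = 10% | 1.00 |
| All dead in both arms | 3/20 = 15% | 3/10 = 30% | 0.372 |
| ADX-629 dead, placebo alive | 3/20 = 15% | 1/10 = 10% | 1.00 |
| ADX-629 alive, placebo dead | 1/20 = 5% | 3/10 = 30% | 0.095 |

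The SAP difference (ADX-629 minus placebo) is −5 points. The data would be compatible with anything from +5 (15 − 10) to −25 (5 − 30). Counting all unknowns as dead in both arms gives −15 and does not reveal the possible reversal; only the arm-opposed rows do.

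On known status only, the rates are 1/18 = 5.6% and 1/8 = 12.5%. A Kaplan-Meier estimate censored at the date last known alive lies between *d*/*n* and this figure, depending on whether the censoring precedes the death. It therefore corrects little if the subjects lost are the sick ones.

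**Illustration B: known deaths 0 vs 2, unknowns 2 vs 1**

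| Treatment of unknowns | ADX-629 | Placebo | Fisher p |
|---|---|---|---|
| SAP: all counted alive | 0/20 = 0% | 2/10 = 20% | 0.103 |
| All dead in both arms | 2/20 = 10% | 3/10 = 30% | 0.300 |
| ADX-629 dead, placebo alive | 2/20 = 10% | 2/10 = 20% | 0.584 |
| ADX-629 alive, placebo dead | 0/20 = 0% | 3/10 = 30% | 0.030 |

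Three unknown statuses are enough to leave p anywhere from 0.030 to 0.584.

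**The case against.** A reader might infer from 6.6 that withdrawn subjects who miss the early termination visit receive no Day 60 call, and that they have no Day 35 contact either. The documents do not support this. Section 6.6 says who is called; it does not say that others are not. Section 6.5 calls all subjects, and 6.4 gives all subjects a Day 35 contact. What remains is a mismatch between 6.5 and 6.6 that sites could read in two ways.

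A reader might also infer that subjects who stop the drug drop out of sight. Section 4.3 keeps them in follow-up through Day 60 unless they withdraw consent for it. Only leaving the trial, loss to follow-up or refusal of contact creates an unknown.

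There are other routes to vital status. The NIAID score is collected daily to Day 28 and score 1 is death (Protocol 3.1, Appendix C). Staff contact outpatients who do not complete the diary (6.3). Fatal COVID-19 progression must be recorded as an SAE (8.2). These routes should keep the number of unknowns small, but they do not guarantee zero.

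It is also not true that the outputs are blind to missing follow-up. SAP 3.3.1 tabulates early study discontinuation and reasons by arm, and SAP 3.4.1 gives n for the NIAID change to Day 28 and lists all NIAID data. A reader could piece together an approximate count. None of these tables states Day 28 vital status or connects it to the mortality rate.

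Finally, the trial is exploratory and unpowered, Fisher's test applies only where applicable, and the deaths and unknowns above are assumed. Two unknowns among ten placebo subjects would be 20% loss. In Illustration A the reversal leaves p at 1.00. All of this limits the weight of the point. It does not change the arithmetic of the formula.

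**Conclusion.** The point holds as a defect in a stated calculation. SAP 3.4.2 gives a lower bound on Day 28 mortality whenever any vital status is unknown, and neither labels it as one nor tests its sensitivity. The possible understatement is up to 5 percentage points per unknown on ADX-629 and 10 on placebo, assuming arms of about 20 and 10. The total effect cannot be fixed in advance, because the documents give no dropout or mortality rate; with no unknowns it is zero.

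The gap does not depend on how 6.6 is read: an unanswered call or withdrawn consent for follow-up produces it too. Separately, 6.5 and 6.6 should be reconciled, and the Day 60 procedure list does not name the item that the call exists to collect. The change is worth making before database lock, but it concerns one of several secondary endpoints in an exploratory trial.

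**What to change.** **Protocol.** Reconcile 6.6 with 6.5 so that vital status is sought for every randomized subject whose consent allows it, whether or not an early termination visit took place. Add vital status (at Day 28 and at the time of the call) and the date last known alive to the procedures in 6.5.

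**SAP 3.4.2.**

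1. Estimate Day 28 mortality by Kaplan-Meier, censoring at the date last known alive.
2. Report by arm the number of subjects with unknown Day 28 vital status.
3. Give bounds: all unknowns alive, all dead, and the two arm-opposed cases (ADX-629 unknowns dead with placebo unknowns alive, and the reverse). Kaplan-Meier alone is not enough because the censoring may be informative, and the all-dead bound alone can miss a reversal.

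**Cost.** A few words in the protocol, a call to any affected subject who would not otherwise have had one, a few sentences in the SAP and one small table. The reported mortality may be slightly less favourable. With no unknowns, the Kaplan-Meier estimate equals deaths over randomized and the reported rate is unchanged.

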### **3.5 Pharmacodynamic (PD) Assessment**

The PD endpoints include the following:

- RASP plasma concentrations; and
- Plasma exploratory biomarker concentrations (e.g., interleukin [IL]-1 $\beta$ , IL-6, IL-10, and tumor necrosis factor alpha).

For each PD parameter, descriptive statistics (n, mean, standard deviation, median, minimum, maximum) will be summarized by treatment group for the PD Population at pre-dose and post-dose of each scheduled visit.

A MMRM analysis similar to that of the key efficacy endpoints will be used for the analysis of PD endpoints as appropriate.

### **3.6 Safety Assessment**

Safety data will be summarized by actual treatment received (and in total for selected analyses) based on the Safety Population.

#### *3.6.1 Adverse Events (AEs)*

AEs will be captured from the date of informed consent through study completion. All AEs will be coded to system organ class and preferred term using MedDRA version 23.1.

Treatment-emergent adverse events (TEAEs) are defined as AEs that start after the first dose of study drug. AEs with partially missing onset dates will also be included as treatment emergent when the month (if it exists) and the year occur on or later than the month and year of the first dose date.

An overview of AEs will be provided including counts and percentages of subjects (and event counts) with the following:

- Any TEAEs (overall and by maximum severity)

- Any study drug related TEAEs
- Any serious AEs (SAEs)
- Any treatment-emergent serious AEs (TESEAEs)
- Any TEAEs leading to discontinuation of study drug
- Any AEs leading to death

Counts and percentages of subjects (and event counts) will also be presented by system organ class and preferred term for each of the categories in the overview.

Listings will be presented for all AEs and hospitalization data.

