6.2 Screening Visit (Day -3 to 1)

The following procedures will be performed at Screening (Day -3 to 1):

- Obtain informed consent;
- Review inclusion and exclusion criteria;
- Obtain demographic information;
- Obtain medical/surgical history;
- Assess NIAID score (see Appendix C);
- Measure weight and height and calculate body mass index;
- Perform full physical examination;
- Measure vital signs;
- Perform PCR or another commercial or public health assay for SARS-CoV-2, and perform a confirmatory test for SARS-CoV-2 (if not done within 3 days [72 hours] of randomization), only if no documented, laboratory-confirmed SARS-CoV-2 infection test result is available;
- Perform serum hCG test (WCBP only);
- Perform FSH testing (naturally postmenopausal women only);
- Perform HIV, HBsAg, and HCV testing, only if status is unknown;
- Perform clinical laboratory assessments;
- Perform 12-lead electrocardiogram (ECG);

Note: ECG may be performed on Day 1, if not done at Screening, but it must be performed before the first dose of study drug is given.

- Perform chest X-ray;
- Record concomitant medications; and
- Record AEs.

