8.1 Adverse Events

An AE is defined as any untoward medical occurrence in a clinical investigation subject administered a pharmaceutical product, which does not necessarily have a causal relationship with this treatment. An AE can therefore be any unfavorable and/or unintended sign (including an abnormal laboratory finding), symptom, or disease temporally associated with the use of an investigational medicinal product, whether or not related to the investigational medicinal product. All AEs, including observed or volunteered problems, complaints, or symptoms, are to be recorded on the appropriate eCRF.

AEs, which include clinical laboratory test variables, will be monitored and documented from the time of informed consent until the last clinical trial visit, including the telephone follow-up. Subjects should be instructed to report any AE that they experience to the Investigator, whether or not they think the event is due to clinical trial treatment. Beginning at Screening, Investigators should make an assessment for AEs at each visit and record the event on the appropriate AE eCRF.

Wherever possible, a specific disease or syndrome rather than individual associated signs and symptoms should be identified by the Investigator and recorded on the eCRF. However, if an observed or reported sign or symptom is not considered a component of a specific disease or syndrome by the Investigator, it should be recorded as a separate AE on the eCRF. Additionally, the condition that led to a medical or surgical procedure (e.g., surgery, endoscopy, tooth extraction, or transfusion) should be recorded as an AE, not the procedure itself.

Any medical condition already present at Screening should be recorded as medical history and should not be reported as an AE unless the medical condition or signs or symptoms present at baseline changes in severity, frequency, or seriousness at any time during the clinical trial. In this case, it should be reported as an AE.

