Clinically significant abnormal laboratory or other examination (e.g., ECG) findings that are detected during the clinical trial or are present at Screening and significantly worsen during the clinical trial should be reported as AEs, as described below. The Investigator will exercise his or her medical and scientific judgment in deciding whether an abnormal laboratory finding or other abnormal assessment is clinically significant. Clinically significant abnormal laboratory values occurring during the clinical trial will be followed until repeat tests return to normal, stabilize, or are no longer clinically significant. Abnormal test results that are determined to be an error should not be reported as an AE. Laboratory test results that are abnormal, but not clinically significant

as determined by the Investigator, should not be reported as an AE. Laboratory abnormalities or other abnormal clinical findings (e.g., ECG abnormalities) should be reported as an AE if any of the following are applicable:

- If an intervention is required as a result of the abnormality;
- If action taken with the study drug is required as a result of the abnormality; or
- Based on the clinical judgment of the Investigator.

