8.1.3 Assessment of Adverse Events by the Investigator

The Investigator will assess the severity (intensity) of each AE using the CTCAE version 5.0 and will also categorize each AE as to its potential relationship to study drug using the categories of “no” or “yes.”

Severity assessment

The severity of all AEs should be graded according to the CTCAE version 5.0. For those AE terms not listed in the CTCAE, the following grading system should be used:

- CTCAE Grade 1: Mild; asymptomatic or mild symptoms; clinical or diagnostic observations only; intervention not indicated;
- CTCAE Grade 2: Moderate; minimal local or noninvasive intervention indicated; limiting age-appropriate instrumental activities of daily living;
- CTCAE Grade 3: Severe or medically significant but not immediately life-threatening; hospitalization or prolongation of hospitalization indicated; disabling; limiting self-care activities of daily living;
- CTCAE Grade 4: Life threatening consequences; urgent intervention indicated; and
- CTCAE Grade 5: Death related to the AE.

Causality assessment

The relationship of an AE to the administration of the study drug is to be assessed according to the following definitions:

- No (unrelated, not related, or unlikely to be related) – The time course between the administration of study drug and the occurrence or worsening of the AE rules out a causal

relationship and another cause (e.g., concomitant drugs, therapies, complication) is suspected; or

- Yes (possibly related, probably related, or definitely related) – The time course between the administration of study drug and the occurrence or worsening of the AE is consistent with a causal relationship and no other cause (e.g., concomitant drugs, therapies, complications) can be identified. The definition implies a reasonable possibility of a causal relationship between the event and the study drug. This means that there are facts (evidence) or arguments to suggest a causal relationship.

The following factors should also be considered when assessing the relationship of an AE to the study drug:

- The temporal sequence from study drug administration;
The event should occur after the study drug is given. The length of time from study drug exposure to event should be evaluated in the clinical context of the event.
- Underlying, concomitant, intercurrent diseases;

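### SAP 3.6.1 defines treatment emergence by start date alone, so an AE that begins between consent and first dose and worsens on drug is left out of the TEAE tables

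*SAP*

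**What the plan says.** The SAP definition (3.6.1) is: "Treatment-emergent adverse events (TEAEs) are defined as AEs that start after the first dose of study drug". Its only extension concerns incomplete dates: "AEs with partially missing onset dates will also be included as treatment emergent when the month (if it exists) and the year occur" in or after the month and year of the first dose. Worsening is not mentioned.

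The protocol treats worsening as a safety event in three places:

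- Section 8.1 says a condition already present at Screening counts only as medical history, "unless the medical condition or signs or symptoms present at baseline changes in severity, frequency, or seriousness at any time during the clinical trial".
- Section 8.1 also says that clinically significant laboratory or other examination findings, such as ECG findings, that "are present at Screening and significantly worsen during the clinical trial should be reported as AEs".
- Section 8.1.3 counts an AE as related when, among other things, "The time course between the administration of study drug and the occurrence or worsening of the AE is consistent with a causal relationship".

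AEs can be on file before dosing. Under Protocol 8.1 they "will be monitored and documented from the time of informed consent until the last clinical trial visit, including the telephone follow-up". Section 6.2 places Screening at Day -3 to 1 and includes AE recording among its procedures.

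**The concern.** Safety is the primary endpoint, and AEs are the first component listed for it (Protocol 7.1). The AE overview in SAP 3.6.1 has six rows, and four of them admit only treatment-emergent events. Each row is also broken down by system organ class and preferred term.

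A start-date test sorts events by when they began, not by what happened on drug. An investigator could judge the worsening of an existing AE to be drug related under Protocol 8.1.3, and the SAP would still keep that AE out of the related-TEAE row because it began before the first dose. For conditions that predate Screening, the count depends on which date a site enters for the same clinical course.

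**Working it through.** The plan states no figure to reproduce. The check is a comparison of the rules, followed by one division for scale.

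**Applying SAP 3.6.1 to five cases** (the days and grades are illustrative):

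1. *An AE starts on Day -2 at Grade 1, reaches Grade 3 on Day 10, and stays on one record.* The start is before the first dose, so it is not a TEAE. Neither document asks for a new record when an existing AE worsens, so this exclusion follows from the stated rule.
2. *A condition present at Screening worsens on Day 10, and the site dates the AE to Day 10.* The start is after the first dose, so it is a TEAE.
3. *The same condition, but the site enters the original onset date.* It is not a TEAE. Neither document says which date applies.
4. *An AE has a complete Day 1 date but no time.* The date is not partially missing, so the incomplete-date rule does not apply. The main rule requires a start after the dose, which the date alone cannot show. The event is unclassified.
5. *An AE has only a month and year, matching the month of first dose.* It counts as a TEAE even if it began before dosing. The SAP is thus inclusive where timing is unknown, but it excludes case 1, where the worsening on drug is known.

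**Effect on the overview rows in SAP 3.6.1:**

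| Row | Limited to treatment-emergent events? |
|---|---|
| Any TEAE, overall and by maximum severity | Yes |
| Related TEAEs | Yes |
| SAEs | No |
| Treatment-emergent SAEs | Yes |
| TEAEs leading to discontinuation | Yes |
| AEs leading to death | No |

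Four of six rows are restricted. A non-serious case 1 event reaches none of the six. A serious one reaches the SAE row but not the treatment-emergent SAE row.

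**Scale.** Inputs are about 30 subjects randomized 2:1 (SAP 2.2.4).

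- ADX-629: 30 × 2/3 = 20, so one subject is 1/20 = 5 percentage points.
- Placebo: 30 × 1/3 = 10, so one subject is 1/10 = 10 percentage points.

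In the any-TEAE row these figures apply only if the subject has no other TEAE. If the subject has another, milder TEAE, the row is unchanged but the maximum-severity count places the subject in too low a grade. The documents give no rate for such events, so an expected number affected cannot be calculated.

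**The case against.** The strongest objection is that most pre-existing illness is already handled. Under Protocol 8.1 a condition present at Screening is not an AE until it changes. On the natural reading the AE comes into being at the change, and a change on drug satisfies the SAP rule. That is correct, and it confines the certain loss to AEs that arise in the short interval between consent and first dose. The COVID-19 symptoms subjects bring to Screening follow the medical-history route and are lost only if a site backdates them.

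Information also survives elsewhere. SAEs and fatal AEs have unrestricted rows, and all AEs are listed, which is readable for about 30 subjects. SAP 3.6.2 counts clinically significant post-baseline laboratory results, and SAP 3.6.3 summarizes change from baseline in vital signs. This stands, but only in part:

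- A listing does not give a rate by arm.
- The SAE row is narrowed by Protocol 8.2, which keeps clear COVID-19 progression out of SAE reporting unless it is drug related or fatal.
- The laboratory tables count abnormal results, not how far a value moved from baseline.

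The dating convention may be set in eCRF completion procedures or in the separate programming specifications (Protocol 11.4, SAP 7), which are not available here. That could settle cases 2 to 4. It would settle case 1 only if it required a new record for each worsening.

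A reader might infer three stronger things that the documents do not support:

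- *That TEAE rates will be too low, or that worsening is a main route by which toxicity would appear.* No event rate is given, so neither is shown.
- *That the comparison between arms is biased.* Treatment assignment is blinded (Protocol 5.3), and nothing suggests that dating practice would differ by arm.
- *That SAP section 6 omits a departure from the protocol.* Protocol 9.2.2 uses the term TEAE but the protocol does not define it, and Protocol 8.1 is a reporting rule. The SAP supplies a definition and changes no specified analysis.

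**Conclusion.** The concern holds in a limited form. By its stated rule, SAP 3.6.1 excludes from the four TEAE-based rows any AE that begins between consent and first dose and worsens on drug, although the protocol treats worsening as reportable and possibly drug related. A condition present at Screening that worsens is excluded only if its original onset date is entered. The main gap is non-serious worsening, together with serious worsening in the treatment-emergent rows. Untimed Day 1 events are a smaller, separate ambiguity.

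The number of subjects affected is unknown and may be zero. The scale of 5 or 10 percentage points per subject assumes arms of about 20 and 10 and, for the any-TEAE row, no other TEAE in that subject. The conclusion on case 1 assumes that a continuing AE stays on one record with its original start date, since nothing in either document says otherwise. The trial is exploratory, but these tables summarize its primary endpoint and the correction is inexpensive, so it should be made.

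**What to change.** Make two linked changes before database lock, which is the point by which SAP 1 requires the plan to be final, and therefore before unblinding.

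1. **SAP 3.6.1.** Define a TEAE as an AE with onset on or after the first dose, or an AE or condition present before the first dose that worsens in severity, frequency or seriousness after it. Add that an AE dated Day 1 without a time counts as treatment-emergent unless it is recorded as starting before the dose.
2. **eCRF completion guideline.** Have sites enter each worsening as a new record dated to the worsening. Without this, or an equivalent dated severity change, the new clause cannot be applied to a record that holds one pre-dose onset date and one grade.

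The cost is a short SAP edit and a small data-entry convention. Any AE already recorded with a pre-dose start that continued past the first dose would need a check for later worsening. No new assessments are required. TEAE counts may rise slightly.
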